#### b. Secondary Objective

Descriptive data will be computed for the real-time fatigue scores, PROMIS Fatigue, and PROMIS Sleep disturbance. Preliminary analysis will be conducted using a two-sided independent samples *t*-tests comparing PROSPER with digital vital sign monitoring (experimental group) compared to PROSPER without digital vital sign monitoring (control group) over the course of the hospitalization.

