#### 3.7 Patient Allocation to study groups

There is generally one patient per room and patient assignment to a room is largely driven by unit census (i.e., bed availability) as well as other clinical factors: e.g., need for an isolation room, nursing availability. All of these factors vary independently of the preferences of the patient or research team, reducing the risk for systematic bias. The unit of randomization is by pod on a floor. Research coordinators as part of the "on-boarding process" will also provide culturally competent instructions and in-person teaching for device use.

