#### 4.3 Research Plan

- a. *Study Population:* In order to participate in the sub-study, participants must be enrolled in the PROSPER trial. We plan to enroll 100 participants from the parent trial in this pilot study, 50 participants from each arm of the parent trial. The inclusion and exclusion criteria for the sub-study are the same as the parent trial.
- b. *Inclusion criteria:* Adult patients (> 18 years of age), English-speaking and able to complete consent and survey materials are eligible to participate. Potential participants must be admitted to the hospital for an anticipated minimum of 3 nights.
- c. *Exclusion criteria:* Vulnerable populations (pregnant, incarcerated, history of delirium, suicidal ideation, ischemic stroke with measurable neurologic deficit, cerebral palsy, seizures), primary brain tumor/metastases patients) are not eligible. Patients concurrently enrolled in contact isolation with SARS-CoV2 will be excluded. Lastly, hospice or hospice-bound patients will also be excluded. Any patient can remove themselves from the study at any point.

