#### 4.4 Study Methods

- a. Study design: The pilot sub-study will be integrated into the parent trial. This pilot study leverages a twogroup, pre-post test design to conduct preliminary tests for differences between the experimental arm (PROSPER intervention with digital vital sign monitoring) and the control arm (PROSPER intervention without digital vital sign monitoring) on objective sleep parameters and patient reported sleep disturbances and fatigue.
- b. Recruitment: Once participants are enrolled in the parent trial, they will be evaluated for inclusion in the pilot sub-study based on the availability of the device that measures objective sleep parameters (Actiwatch Spectrum Pro®). Thirty wrist actigraphy devices (Actiwatch Spectrum Pro®) are available for use at any given time. Fifty participants from the patient care units designated as the intervention arm for the parent trial will be enrolled as treatment patients in the substudy; fifty participants from the patient care units designated as the control arm will be enrolled as control patients in the substudy. Participants will be consecutively enrolled in the sub-study as they are enrolled in the parent study although enrollment may pause if wrist actigraphy devices are not available.
- c. Instrumentation: Objective sleep parameters will be assessed with the Actiwatch Spectrum Pro® during the course of hospitalization, consistent with the parent trial. Patient-reported sleep disturbances will be measured with the PROMIS Sleep Disturbance Adult Short Form. Patient-reported fatigue will be measured in real-time with a one-time global fatigue intensity rating over the course of the hospitalization and the PROMIS Fatigue Adult Short Form. The PROMIS instruments will be completed upon enrollment and discharge +/- 1 day, consistent with the parent trial.

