Fatigue	Patient-Reported Real-Time Assessments over course of hospitalization (Actiwatch		
	Spectrum Pro)		
	• 1-item fatigue intensity scale using the subjective event marker of the		
	Actiwatch Spectrum Pro		
	Patient-Reported Questionnaires		
	PROMIS Fatigue Adult Short Form		
Sleep	Patient-Reported Questionnaires		
Disturbances	PROMIS Sleep Disturbance Adult Short Form		
	Objective Real-Time Assessment averaged over the time of hospitalization		
	(Actiwatch Spectrum Pro)		
	Total Sleep Time		
	Sleep Latency (minutes until sleep onset)		
	Sleep Efficiency		
	
 
Frequency and Duration of Awakenings after sleep onset (WASO)
 
		
	Number of Awakenings		

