#### 4.4 Data Collection

Upon enrollment to the pilot sub-study, the wrist actigraph will be placed on the non-dominant wrist. The research staff will review real-time fatigue intensity rating procedures and instruct participants to leave the device in place for the duration of the hospitalization. Participants will be directed to carry on with normal activities. They will be asked to rate the intensity of fatigue at that moment in time on a 0 (no fatigue) to 10 (worst fatigue) scale five times during each day (upon awakening, 10:00 am, 2:00 pm, 6:00 pm, and at bedtime). An audible and vibratory alarm on the wrist actigraph will sound at preset times (10:00 am, 2:00 pm, and 6:00 pm) to remind participants to complete the real-time fatigue assessment. They will enter the rating directly into the subjective event marker of the wrist actigraph. Because of the expected time variability associated with awakening and going to bed, it will not be possible to program the Actiwatch Spectrum Pro® to alarm at these times. Participants will complete the PROMIS Sleep Disturbance and Fatigue questionnaires upon enrollment and hospital discharge +/- 1 day, in keeping with the parent trial data collection periods.

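### Real-time fatigue is compared over the whole stay with no defined start, so ratings made before the first ViSi night can count as outcome and the same-scale baseline goes unused

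*Combined protocol and SAP*

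**What the plan says.** All references are to the combined protocol and SAP.

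- **Analysis (4.5, b. Secondary Objective).** "Preliminary analysis will be conducted using a two-sided independent samples" t-tests, setting the monitored arm against "PROSPER without digital vital sign monitoring (control group) over the course of the hospitalization". No covariate, start point or baseline is named for real-time fatigue.
- **Start and frequency of ratings (4.4 Data Collection).** "Upon enrollment to the pilot sub-study, the wrist actigraph will be placed on the non-dominant wrist". Patients then rate fatigue from 0 to 10 "five times during each day (upon awakening, 10:00 am, 2:00 pm, 6:00 pm, and at bedtime").
- **Window (variables table in 4.4 Study Methods).** "Patient-Reported Real-Time Assessments over course of hospitalization", with no separate baseline entry.
- **Design label (4.4 Study Methods, a).** A two-group "pre-post test design to conduct preliminary tests for differences between the experimental arm" and the control arm.
- **Adjustment elsewhere.** Exploratory ANCOVA with baseline measures and length of stay appears only under the primary objective (4.5a), for the sleep parameters.
- **Start of ViSi wear.** Not stated. Section 3.7 says only that coordinators give "in-person teaching for device use" as part of on-boarding. Section 4.4 Study Methods, b, describes sub-study entry both as following parent enrolment and as running alongside it.
- **Size and allocation.** "50 participants from each arm of the parent trial" (4.3), with the arm set by the unit to which the patient is admitted (3.4).

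**The concern.** The device replaces night-time vital sign checks, so any benefit for fatigue should come through better-protected nights. Ratings made before a patient's first ViSi night cannot show that benefit. If they are averaged with later ratings, they pull the estimated difference toward zero, most strongly in short stays.

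The same ratings have a better use. Allocation follows bed availability and is not randomised. A fatigue score on the same 0 to 10 scale, taken before exposure, is the most direct check on prior differences between the arms. The sub-study calls itself pre-post, yet its analysis of this measure uses no pre value. PROMIS Fatigue has an enrolment value, but it is a different instrument with 7-day recall.

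**Working it through.** The plan states no effect size, SD or power for real-time fatigue, so there is no figure of its own to reproduce. The steps below show what its wording implies.

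**1. Share of ratings before the first study night**

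From the documents: five ratings per full day (4.4 Data Collection), a minimum stay of 3 nights (3.2; anticipated in 4.3), and approach in the first one to two days (3.5). Assumed: midday enrolment, leaving 3 ratings that day (2 pm, 6 pm, bedtime), and midday discharge, giving 2 that day (awakening, 10 am).

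For a stay of L nights enrolled a days after admission, the total is 3 + 5 × (L − 1 − a) + 2, and the share is w = 3 / total.

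| Nights | a = 0 | a = 1 | a = 2 |
|---|---|---|---|
| 3 | 3/15 = 20% | 3/10 = 30% | 3/5 = 60% |
| 5 | 3/25 = 12% | 3/20 = 15% | 3/15 = 20% |
| 7 | 3/35 = 9% | 3/30 = 10% | 3/25 = 12% |

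Time of enrolment matters. For a 3-night stay with a = 1, one enrolment-day rating gives 1/8 = 12.5%, and four give 4/11 = 36%.

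**2. Effect of pooling**

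If each patient's ratings are simply averaged, the expected arm difference is (1 − w) times the effect after the first night. The variance also changes. With equal SDs for the early and later means and correlation ρ between them, the standardised effect is multiplied by

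(1 − w) / √[(1 − w)² + w² + 2w(1 − w)ρ].

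At w = 0.20 and ρ = 0.5 this is 0.80 / √(0.64 + 0.04 + 0.16) = 0.80 / 0.917 = 0.873.

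For power, take 50 per arm and two-sided alpha 0.05 (assumed; none is stated). Set the reference effect so that ratings after the first night alone give 80% power: d = (1.960 + 0.842) × √(2/50) = 0.56. With one common w for all patients and ρ = 0.5, pooled power is:

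- w = 0.09: 76%
- w = 0.20: 69%
- w = 0.30: 60%

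Over ρ from 0.3 to 0.7, the ranges are 74% to 77%, 65% to 72%, and 56% to 65%.

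**3. Gain from using the early ratings as baseline**

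ANCOVA raises the standardised effect to d / √(1 − ρ²). From 80% without adjustment, power becomes:

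- ρ = 0.3: 84%
- ρ = 0.5: 90%
- ρ = 0.7: 97.5%

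**4. What happens if the baseline is not clean**

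Suppose a fraction f of intervention patients had already spent a ViSi night before their first rating, and that this shifts the baseline by the full effect. The adjusted estimate is then about 1 − slope × f of the true effect. With an assumed covariate slope of 0.66:

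- f = 0.25: 1 − 0.165 = 0.835
- f = 0.50: 1 − 0.33 = 0.67
- f = 1: 0.34

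The unadjusted mean after the first night stays at 1. Adjustment therefore helps only if the baseline is anchored to the first ViSi night.

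**The case against.** **The device may already be in use.** No section says when ViSi wear begins, and sub-study entry can wait for a free actigraph. A reader might infer that all enrolment-day ratings precede the device; the documents do not establish that. For a patient with an earlier ViSi night, those ratings are neither dilution nor baseline, and adjusting for them does the harm shown in step 4. This stands, and it shapes the fix.

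**Averaging is not stated.** The whole-stay phrase also covers PROMIS, which is collected only at enrolment and discharge, and 4.4 Study Methods, c, describes the fatigue rating as a single one. The per-patient summary is undefined, so dilution depends on averaging being the choice made. It is the natural reading, but only a reading. The objection does not remove the need to define the window.

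**A whole-stay mean is a legitimate quantity.** It is attenuated only relative to the effect from the first ViSi night onward. That is fair, but the latter is what the rationale for the device describes.

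**The size can be overstated.** A reader might take 60% as typical or expect near-certain power from adjustment. The first needs the minimum stay with the latest approach. The second needs a correlation of about 0.7 or more, which the documents do not supply, and a single afternoon's fatigue in surgical and medical inpatients may predict less well.

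**Conclusion.** The point holds in a conditional form. As written, 4.5b lets ratings from before the first ViSi night count as outcome and leaves the only same-scale baseline unused in a comparison of non-randomised units. Dilution under simple averaging with midday enrolment and discharge is 20% to 60% for a 3-night stay and roughly 9% to 20% for 5 to 7 nights. It applies only to patients whose actigraph is placed before their first ViSi night. The gain from adjustment is positive but uncertain: from 80% to between 84% and 97.5% for assumed correlations of 0.3 to 0.7.

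The documents do not support saying that the planned estimate is badly biased. This is a preliminary secondary analysis in a pilot with no stated power for fatigue, and the early ratings remain stored for reanalysis. The case for change is that a better-defined analysis is available at almost no cost.

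**What to change.** In 4.5b:

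1. Define the outcome as each patient's mean of ratings from the first awakening after the first study night. For the intervention arm, this is the first night with ViSi in use after enrolment; for controls, the first night after enrolment.
2. Analyse by ANCOVA with arm and the mean of ratings entered before that night.
3. Record the times of ViSi start and actigraph placement. Never use a rating made after a ViSi night as baseline; treat that patient's baseline as missing.
4. Report the unadjusted comparison of ratings after the first study night as a sensitivity analysis.
5. State a rule for intervention patients who never have a ViSi night. Using the first night after enrolment would keep them in the analysis, in line with the intent-to-treat framework of section 3.10.
6. Reconcile the single rating in 4.4 Study Methods, c, with the five a day in 4.4 Data Collection.

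**Cost.** SAP wording and two recorded times; no added patient burden. Ratings are held in the actigraph's memory, and ViSi data are linked by time stamp and device ID (3.8). That each fatigue entry carries a time is not stated and should be confirmed.

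**Downside.** Some baselines will rest on few ratings or be missing and need imputation. Those set to missing because of an earlier ViSi night will fall only in the intervention arm, which is why the unadjusted result should be shown alongside.

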#### 5.0 Risks/Benefits

The parent study poses minimal risks to patient's well-being in light of the fact that they will still be receiving standard of care per hospital routine that is augmented by novel technologies (i.e., passive vital signs monitoring). Although not anticipated, there may also be a minimal risk of emotional distress in patients when answering questions about depression and anxiety (HADS scale). However, study participation is completely voluntary, and participants may opt to skip any/all questions in the survey that they do not feel comfortable answering. Finally, we believe that any possible risks will be counterbalanced by potential benefits to study participants such as new insights, potential to help others, feelings of wellbeing and an opportunity to discuss their inpatient care journey.

This pilot sub-study is a minimal risk study. The risk of wearing the wrist actigraph device is minimal but may include skin irritation from the wristband. The risks associated with wearing a wrist actigraph are the same as wearing a wristwatch. In all of our studies that measured physical activity and sleep with wrist actigraphy, only one subject complained of skin irritation from the wristband. The skin irritation was minimal, did not require treatment, and was rectified using a different wristband. The subject continued in the study. No other subjects complained of skin irritation. There is minimal risk associated with self-reported assessments (fatigue and sleep disturbances). Providing these data may cause subjects some emotional discomfort. In our previous studies using these measures, no subjects reported emotional discomfort and/or distress.

#### 6.0 Data Confidentiality Plan

The study team is committed to protecting patient confidentiality at all times and in all circumstances. No patient identifying information will be used in the publication of findings and all information extracted from the medical record will be entered onto coded data sheets which will be maintained on Excel spreadsheets stored in approved locations and accessible by MDACC employees. Electronic data will be strictly stored only on password protected institutional computers and/or electronic databases behind the MD Anderson firewall and accessible only to the PI and collaborators. If needed, hard copies of the coded study will be stored in a locked cabinet in the principal investigator's or study manager's office. Only the PI and the collaborators will be participating in the collection and analysis of data. No patient identifying information will be used in presentation or publication of this material. Upon study termination, all data, questionnaires and remaining identifiers will be banked indefinitely in REDCap for future use only in IRB-approved research. The technology vendor (Sotera Wireless) will have no access to patient confidential information (name, medical history, demographics, treatment history). All the vital sign data captured on the ViSi mobile passive monitoring device are captured and transmitted in an anonymized fashion.

A contractual agreement will be reached between Sotera and MD Anderson regard data usage and will be subject to approval by MD Anderson legal counsel to specify the following: Unless necessary to use the Products or Professional Services, Hospital agrees to not submit to Company: (i) any personally identifiable information; (ii) any protected health information regulated by the U.S. Health Insurance Portability and Accountability Act ("HIPAA") or any similar federal, state, or local laws, rules, or regulations; or (iii) any information subject to regulation or protection under the Gramm-Leach-Bliley Act. Hospital acknowledges that any submission to Company contrary to the foregoing statement is at Hospital's own risk. In performing any Professional Services, Company may receive from Hospital patient healthcare, billing, or other confidential patient information ("Patient Information"). Hospital will identify to Company in writing all such information when Hospital provides such information to Company and Company will use Patient Information so identified by Hospital only as necessary to provide the Professional Services to Hospital. Company will treat Patient Information consistently with all applicable laws and regulations and in accordance with the Business Associate Agreement entered by the Parties concurrently with this Addendum or immediately prior to Company performing any Service. Hospital represents and certifies that Hospital has received appropriate consents to provide such Patient Information to Company. Hospital agrees to not interrogate, or extract data from any Company product without written consent from Company

### Appendix – Surveys

#### Patient Activation Measure

1.	I am the person who is responsible for taking care of my health.	Disagree Strongly	Disagree	Agree	Agree Strongly	N/A
2.	Taking an active role in my own health care is the most important thing that affects my health.	Disagree Strongly	Disagree	Agree	Agree Strongly	N/A
3.	I am confident I can help prevent or reduce problems associated with my health.	Disagree Strongly	Disagree	Agree	Agree Strongly	N/A
4.	I know what each of my prescribed medications do.	Disagree Strongly	Disagree	Agree	Agree Strongly	N/A
5.	I am confident that I can tell whether I need to go to the doctor or whether I can take care of a health problem myself.	Disagree Strongly	Disagree	Agree	Agree Strongly	N/A
6.	I am confident that I can tell a doctor or nurse concerns I have even when he or she does not ask.	Disagree Strongly	Disagree	Agree	Agree Strongly	N/A
7.	I am confident that I can carry out medical treatments I may need to do at home.	Disagree Strongly	Disagree	Agree	Agree Strongly	N/A
8.	I understand my health problems and what causes them.	Disagree Strongly	Disagree	Agree	Agree Strongly	N/A
9.	I know what treatments are available for my health problems.	Disagree Strongly	Disagree	Agree	Agree Strongly	N/A
10.	. I have been able to maintain lifestyle changes, like healthy eating or exercising.	Disagree Strongly	Disagree	Agree	Agree Strongly	N/A
11.	I know how to prevent problems with my health.	Disagree Strongly	Disagree	Agree	Agree Strongly	N/A
12.	I am confident I can work out solutions when new problems arise with my health.	Disagree Strongly	Disagree	Agree	Agree Strongly	N/A
13.	I am confident that I can maintain lifestyle changes, like healthy eating and exercising, even during times of stress.	Disagree Strongly	Disagree	Agree	Agree Strongly	N/A

Insignia Health. "Patient Activation Measure; Copyright © 2003-2015, University of Oregon. All Rights reserved." Contact Insignia Health at www.insigniahealth.com

#### **Richards-Campbell Sleep Questionnaire**

You are now ready to begin to answer the questions. Place your "X" anywhere on the answer line that you feel best describes your sleep last night.

1. 1	dy sleep last night was:	
	Deep Sleep	Light Sleep

2. Last night, the first time I got to sleep, I:

Fell	Just Never
Asleep	Could Fall
Almost	Asleep
Immediately	

3. Last night I was:

Awake	
Very	Awake All
Little	Night Long

4. Last night, when I woke up or was awakened, I:

Got Back	Couldn't
To Sleep	Get Back To
Immediately	Sleep

5. I would describe my sleep last night as:

A Good	A Bad
Night's	Night's
Sleep	Sleep

nsidered

2022-0190 v.23Mar2023 Page 14 of 18

Hospital Anxiety and Depression Scale (HADS) Instructions: Doctors are aware that emotions play an important part in most illnesses. If your doctor knows about these feelings he or she will be able to help you more. This questionnaire is designed to help your doctor know how you feel. Read each item and circle the reply which comes closest to how you have been feeling in the past week. Don't take too long over your replies: your immediate reaction to each item will probably be more accurate than a long thought out response.

I feel tense or 'wound up':	A	I feel as if I am slowed down:	D
Most of the time	3	Nearly all of the time	3
A lot of the time	2	Very often	2
Time to time, occasionally	1	Sometimes	1
Not at all	0	Not at all	0
I still enjoy the things I used to enjoy:	D	I get a sort of frightened feeling like 'butterflies in the stomach':	A
Definitely as much	0	Not at all	0
Not quite so much	1	Occasionally	1
Only a little	2	Quite often	2
Not at all	3	Very often	3
get a sort of frightened feeling like something awful is about to happen:	A	I have lost interest in my appearance:	D
Very definitely and guite badly	3	Definitely	3
res, but not too badly	2	I don't take as much care as I should	2
A little, but it doesn't worry me	1	I may not take guite as much care	1
Not at all	0	I take just as much care as ever	0
can laugh and see the funny side of things:	D	I feel restless as if I have to be on the	A
As much as I always could	0	Very much indeed	3
Not quite so much now	1	Quite a lot	2
Definitely not so much now	2	Not very much	1
Not at all	3	Not at all	0
Worrying thoughts go through my mind:	Α	I look forward with enjoyment to things:	D
A great deal of the time	3	A much as I ever did	0
A lot of the time	2	Rather less than I used to	1
From time to time but not too often	1	Definitely less than I used to	3
Only occasionally	0	Hardly at all	2
feel cheerful:	D	I get sudden feelings of panic:	A
Not at all	3	Very often indeed	3
Not often	2	Quite often	2
Sometimes	1	Not very often	1
Most of the time	0	Not at all	0
can sit at ease and feel relaxed:	A	l can enjoy a good book or radio or TV programme:	D
	0	Often	0
Definitely	0		
Definitely Usually	1	Sometimes	1
Definitely Usually Not often	1 2	Sometimes Not often	1

